3.2.2.2. Nonclinical Data

Broad antiproliferative effects of prexasertib monotherapy were demonstrated in various tissue culture studies using growth inhibition or clonogenic survival in soft agar as a phenotypic endpoint. A panel of 621 genomically characterized tumor cell lines derived from multiple cancer types and various histologies were tested. Prexasertib showed widespread antiproliferative effects; growth of 66% of these lines was inhibited at half-maximal inhibitory concentration (IC_{50}) concentrations of ≤ 50 nM. Further, the antiproliferative activity of prexasertib in the subset of 23 cell lines derived from human ovarian cancers showed IC_{50} values that ranged between 2 and 320 nM; 70% (16 of 23) of these lines had IC_{50} values ≤ 50 nM.

Studies in xenograft tumors also demonstrated prexasertib to be a potent inhibitor of tumor cell growth. Studies in the orthotopically implanted intraperitoneal SKOV-3 model using a 3-days-on/4-days-off schedule showed prexasertib monotherapy resulted in a dose-dependent inhibition of tumor growth. At the end of the dosing period (Day 31), inhibition was 52.7% and 70.7% for groups treated with 4 and 12 mg/kg of prexasertib, respectively, compared with vehicle. Necropsy showed dose-dependent reductions in ascites fluid volume and number of tumor colonies (localized metastases) in the peritoneal cavity. These results are concordant with studies of subcutaneous-implanted xenograft such as the A-2780 model, in which tumor growth inhibition at the end of the active dosing period was 60.3%, 63.1%, and 93% after monotherapy with 1, 4, and 12 mg/kg of prexasertib, respectively (McNeely et al. 2011).

3.2.2.3. Clinical Data in Patients with High-Grade Serous Ovarian Cancer

[figure not shown]
The safety profile of prexasertib is consistent with toxicities commonly observed with standard of care cytotoxic agents used to treat cancer. Hematologic toxicity is the most frequent and severe toxicity after treatment with 105 mg/m² prexasertib every 14 days. Nonhematologic toxicity occurs at a lower frequency than hematologic toxicity and has been predominantly Grade 1 or 2 in severity. Complications from hematologic toxicities such as febrile neutropenia, infections, and clinically significant bleeding events have also been observed, but can be mitigated by supportive care approaches such as granulocyte colony stimulating factor (G-CSF) and transfusions. Events with a fatal outcome have occurred following sepsis/infection and clinically significant bleeding. Patients should be closely monitored for signs of infections, sepsis, and bleeding complications. Clinical data from completed and ongoing studies across the

clinical program are summarized in the Investigator's Brochure (IB). Interim data available from 1 study in patients with ovarian cancer are summarized below.

The National Cancer Institute (NCI; principal investigator, [name]) is sponsoring a Phase 2 pilot study with a primary objective of determining the overall response rate (ORR) of prexasertib monotherapy in patients with breast cancer, ovarian cancer, or prostate cancer (NCT02203513, I4D-MC-E001[E001]). Patients receive prexasertib on Days 1 and 15 of a 28-day cycle at the recommended Phase 2 dose (RP2D) of 105 mg/m² (NCI 2017b). Preliminary results from 32 heavily pretreated female patients with HGSOc were presented at the meeting of the European Society for Medical Oncology (ESMO) in October 2016 (Lee et al. 2016). Interim data included 7 patients in Group 1 (with documented deleterious germline *BRCA1/BRCA2* mutation [*gBRCA1/2m*]) and 25 patients in Group 2 (with negative family history of hereditary breast ovarian cancer syndrome or negative *gBRCA1/2m* test) (Lee et al. 2016).

Grade 4 neutropenia was observed in 69% of patients and 75% of the Grade 3 and 4 neutropenia events resolved to Grade ≤ 2 within 8 days after onset; 2 patients (6%) had febrile neutropenia and 56% received G-CSF. Other toxicities included decreased white blood cell (WBC) count (78%), anemia (66%), and decreased platelet count (34%). Nonhematologic adverse events (AEs) included fatigue, nausea, vomiting, and diarrhea (9% each); all were generally mild (Lee et al. 2016). One patient had Grade 3 diarrhea and vomiting during infusion. Only 1 patient (3%) required a dose reduction (80 mg/m²) (Lee et al. 2016).

Figure JTJN.3.1 presents a plot of best responses for target lesions by patient among patients treated with prexasertib. Of the 25 patients treated in Group 2, 20 were evaluable for tumor response. Seven (35%) evaluable patients achieved partial response (PR) (including 2 whose disease was platinum-sensitive and 5 whose disease was platinum-resistant or -refractory). The median duration of response was 6 months (range: 2-13 months), and 5 (25%) patients achieved stable disease (SD) lasting ≥ 4 months, for a DCR of 60%. Patients were heavily pretreated. Platinum-resistant patients had a median of 4 prior lines of therapy (range: 1-13). Of the 7 patients treated in Group 1, 6 were evaluated for tumor response. None of the evaluable patients in Group 1 achieved CR or PR, but 4 (67%) achieved SD lasting ≥ 4 months, for a DCR of 67%. As with Cohort 2, patients had received numerous prior treatments (median: 7, range: 3-12). These preliminary results suggest that prexasertib could be a novel approach to improve the outcomes of patients with HGSOc (Lee et al. 2016).

Abbreviations: *gBRCAm* = germline *BRCA* mutated; HGSOC = high-grade serous ovarian cancer. White bar = platinum-sensitive disease; black bar = platinum-resistant or -refractory disease.

Figure JTJN.3.1 Best response for target lesions, among patients with platinum-sensitive, -resistant, or -refractory disease treated with prexasertib.

3.2.2.4. Rationale for JTJN Cohorts

Patients enrolled in Study JTJN will be assigned to one of 4 cohorts:

- Cohort 1: Platinum-resistant, *BRCA* negative, and received ≥ 3 lines of prior therapy
- Cohort 2: Platinum-resistant, *BRCA* negative, and received < 3 lines of prior therapy
- Cohort 3: Platinum-resistant, *BRCA* positive, there is no restrictions on number of lines of prior therapy, but patients must have received prior PARP inhibitor
- Cohort 4: Platinum-refractory, *BRCA* positive or negative, no restrictions on number of lines of prior therapy.

Patients with *BRCA* test results positive for deleterious or suspected deleterious mutations are referred to as *BRCA* positive, and patients with *BRCA* test results negative for deleterious or suspected deleterious *BRCA* mutations are referred to as *BRCA* negative. Patients with variants of unknown significance should be considered *BRCA* negative.

As described in Section 3.2.2.3, preliminary data from Study E001 suggest clinical benefit of prexasertib in heavily pretreated patients (Lee et al. 2016). To test this hypothesis, Cohort 1 and 2 will segregate patients based on the number of prior lines of therapy. Similarly, Study E001 suggests potential differences in activity in patients with and without *BRCA* mutation. Although data are limited, the cohort of patients without *BRCA* mutation had a higher response rate than those with *BRCA* mutation. The reason for this difference is not clear. Alterations in the HRR pathway, such as *BRCA* mutations, are reported to be mutually exclusive with *CCNE1* amplification (Kroeger and Drapkin 2017). As described in Section 3.2.2.1, *CCNE1* amplification may increase replication stress and result in sensitivity to a CHK1 inhibitor such as prexasertib. Notably, in Study E001 all patients with *BRCA* mutation had been treated with a PARP inhibitor (Lee et al. 2016). Mechanisms of PARP inhibitor resistance that restore HRR may lead to diminished sensitivity to prexasertib; prior treatment with PARP inhibitors could

confound results in *BRCA* mutant patients who are subsequently treated with prexasertib, as tumors in these patients may be proficient for HRR. Note that mechanisms of resistance to PARP inhibitors that do not involve restoration of HRR also have been characterized (Lord and Ashworth 2013; Rondinelli et al. 2017), some of which would not be implicated in cross-resistance to prexasertib. Cohort 3 of Study JTJN was designed to better characterize effects of prexasertib in patients with a *BRCA* mutation who had a prior PARP inhibitor. Study E001 enrolled a cohort of 7 patients with the germline *BRCA* mutation, of which 6 patients had platinum-resistant or –refractory disease (Lee et al. 2016). Cohort 4 in Study JTJN will include platinum-refractory patients to determine any prexasertib benefit in these high-unmet medical need patients.

As described in Section 3.1, gemcitabine, paclitaxel, and PLD are common standard of care agents for HGSOC recurrent disease. The present study, JTJN, could prompt the initiation of a randomized controlled trial that may include investigator's choice of these chemotherapy options as the control arm. Excluding patients (Cohorts 1-3) that have received more than two of these agents for platinum resistant disease is consistent with the entry criteria that are likely to be applied in future studies.

3.3. Benefit/Risk Assessment

Given the high unmet need for additional therapies to treat platinum-resistant or –refractory HGSOC, the mechanistic rationale supporting a role for CHK1 inhibition to improve outcomes for patients with HGSOC, nonclinical model data (including HGSOC) on prexasertib monotherapy, prexasertib clinical safety profile, and preliminary efficacy observed in patients with HGSOC, the risk/benefit assessment supports evaluation of prexasertib monotherapy in the proposed patient population. More information on known and expected benefits, risks, serious adverse events (SAEs), and reasonably anticipated AEs of prexasertib are described in the IB.

4. Objectives and Endpoints

Table JTJN.5 shows the objectives and endpoints of the study.

Table JTJN.5. Objectives and Endpoints

Objectives	Endpoints
Primary	
To estimate the ORR for each cohort	
 • ORR: proportion of all enrolled patients who achieve a best overall response of PR+CR as determined per RECIST version 1.1.
Secondary	
To characterize the safety and toxicity profile of prexasertib	
 • The safety endpoints evaluated will include but are not limited to the following: AEs, SAEs, clinical laboratory tests, ECGs vital signs, and physical examinations
To characterize the PK of prexasertib	
 • Prexasertib concentrations in plasma
To estimate secondary efficacy measures including DCR, DoR, CA-125 response, PFS, OS	
 • DCR: proportion of patients who achieve a best overall response of CR, PR and SD (for at least 4 months) as determined per RECIST version 1.1. • DoR: time from the date measurement criteria for CR or PR (whichever is first recorded) are first met until the first date of documented PD, per RECIST 1.1 criteria, or the date of death from any cause in the absence of documented PD. • CA-125 response: at least a 50% reduction in CA-125 levels from a pretreatment sample that is at least twice the upper limit of the reference range and obtained within 2 weeks before starting the treatment, with confirmation after 4 weeks according to GCIG criteria. • PFS: time from enrollment until the first radiographic documentation (as assessed by the investigator) of progression or death from any cause in the absence of documented PD • OS: time from enrollment until death from any cause
Tertiary/Exploratory	
To assess the relationship between biomarkers, prexasertib exposure (PK), and clinical outcomes	
 • Biomarker research assessed from blood or tissue samples, unless precluded by local regulations • Plasma concentration of prexasertib • Clinical outcomes data
To evaluate patient-reported outcomes using NCCN-FACT-FOSI 18 and Worst Pain NRS	
 • Change from baseline • Time to progression • Association between time to pain progression and analgesic consumption • Association between time to progression and select efficacy outcomes

Abbreviations: AEs = adverse events; CR = complete response; DCR = disease control rate; DoR = duration of response; ECG = electrocardiogram; GCIG = Gynecologic Cancer Intergroup; NFOSI-18 = National Comprehensive Cancer Network – Functional Assessment of Cancer Therapy – Ovarian Symptom Index-18; NRS = numeric rating scale; ORR = overall response rate; OS = overall survival; PD = progressive disease; PFS = progression-free survival; PK = pharmacokinetics; PR = partial response; RECIST = Response Evaluation Criteria In Solid Tumors version 1.1 (Eisenhauer et al. 2009); SAEs = serious adverse events; SD = stable disease.

5. Study Design

5.1. Overall Design

Study I4D-MC-JTJN is a multicenter, nonrandomized, parallel cohort, Phase 2 study in approximately up to 180 patients with high-grade serous ovarian, primary peritoneal, or fallopian tube cancer. Patients will be assigned to the following cohorts:

- Cohort 1: Platinum-resistant, *BRCA* negative, and received ≥ 3 lines of prior therapy
- Cohort 2: Platinum-resistant, *BRCA* negative, and received < 3 lines of prior therapy
- Cohort 3: Platinum-resistant, *BRCA* positive, there is no restriction on number of lines of prior therapy, but must have received prior PARP inhibitor
- Cohort 4: Platinum-refractory, *BRCA* positive or negative, no restrictions on number of lines of prior therapy

Interim analyses will occur at specified intervals. Based on protocol-defined rules, enrollment to a cohort can stop due to lack of efficacy or continue at each interim analysis until the total sample size is reached. See Section 10.3.4 for further details regarding interim analyses.

5.2. Number of Patients

The maximum total sample size of this study is estimated to be approximately 180 patients. For each of the 4 cohorts, the minimum sample size is approximately 20 patients. The sample size for each cohort will be dependent on the outcomes of the interim analyses. As cohorts are halted, new eligible patients will be allocated to the enrolling cohorts. As a result, the maximum sample size of a single cohort is approximately 120 patients (e.g., if enrollment to all but one of the cohorts is stopped after the first interim analysis).

5.3. End of Study Definition

Study completion occurs after the clinical trial database is locked and final analysis of primary and secondary endpoints have been performed. End of the trial is the date of the last visit or last scheduled procedure shown in the Schedule of Activities (Section 2) for the last patient.

5.4. Scientific Rationale for Study Design

An open-label, parallel cohort, nonrandomized Phase 2 study without concurrent controls is appropriate for patients with high-grade serous ovarian, primary peritoneal, or fallopian tube cancer. There is not a clear world-wide standard of care for HGSOc patients with platinum-resistant or platinum-refractory disease. Given the high unmet medical need, this nonrandomized design will enable all participants to receive study drug. The details of the study design are described in Section 5, and details of the sample size determination are provided in Section 10.1.

5.5. Justification for Dose

Based on the nonclinical prexasertib pharmacokinetic (PK)/pharmacodynamic model (inhibition of phosphorylated CHK1 and tumor growth response in Calu-6 xenografts) used to predict the

human efficacious exposure range, the population based PK analysis from the first-in-human dosing (FHD) study JTJA demonstrating that a body surface area (BSA)-based dose regimen is justified for prexasertib administration, the similar systemic exposure and similar safety profile between schedules of administration, as well as the increased patient convenience, 105 mg/m² of prexasertib on Day 1 of a 14-day schedule was selected as the RP2D.

The population PK predicted (from 1000 simulated individual PK profiles) median AUC₍₀₋₇₂₎ (2034 ng•hr/ml) following administration of 105 mg/m² every 14 days is greater than the median AUC₍₀₋₇₂₎ (1896 ng•hr/mL) predicted from a Calu-6 xenograft model before clinical investigation to achieve the maximal tumor response with prexasertib monotherapy. In addition, the average prexasertib plasma concentrations over the first 72 hours (C_{av,72}) predicted from the population PK model from Study JTJA after 105 g/m² (approximately 28 ng/mL) is greater than the IC₅₀ (14.1 ng/mL) determined from the single-agent nonclinical Calu-6 xenograft PK/pharmacodynamic model, also demonstrating that the prexasertib systemic exposure at the R2PD is in a potentially efficacious range. Additional details are described in Sections 5.2.3 and 6 of the IB.

6. Study Population

Prospective approval of protocol deviations to recruitment and enrollment criteria, also known as protocol waivers or exemptions, is not permitted.

6.1. Inclusion Criteria

Patients are eligible to be included in the study only if they meet **all** of the following criteria

- [1] Women who have histologically or cytologically verified high-grade serous ovarian, primary peritoneal or fallopian tube cancer.
- [2] Cohorts 1 to 3: Have platinum-resistant disease, which is defined as disease progression within 6 months of last dose of platinum-based chemotherapy. Progression due to rising CA125 only is not considered as platinum-resistant disease.

Cohort 4: Have primary platinum-refractory disease defined as disease progression during or within 4 weeks after the last dose of initial line of platinum-based chemotherapy.

Note: disease progression may be either radiographic progression or documented clinical progression. Residual disease is not considered progression.

- [3] Cohort 1: Are *BRCA* negative and have received 3 or more prior lines of therapy for high-grade serous ovarian, primary peritoneal, or fallopian tube cancer (including immunotherapy, targeted therapies, or chemotherapy (systemic or intraperitoneal).

Cohort 2: Are *BRCA* negative and have received less than 3 prior lines of therapy for high-grade serous ovarian, primary peritoneal, or fallopian tube cancer (including immunotherapy, targeted therapies, or chemotherapy (systemic or intraperitoneal).

Note for Cohorts 1 and 2: Each line of therapy is preceded by evidence of clinical or radiographic disease progression (initial therapy is considered the first line). Switch of an agent within the same drug class (for example, cisplatin to carboplatin) within a regimen to manage toxicity does not define the start of a new line of therapy.

Similarly, maintenance therapy (continuation maintenance or switch maintenance) will not be considered a new line of treatment. Hormonal therapy is not considered a line of therapy. All adjuvant therapy should be considered as a line of therapy.

Cohort 3: Are *BRCA* positive and have previously received a PARP inhibitor at any time following diagnosis. Note: there is no restriction on number of lines of prior therapy.

Cohort 4: Are *BRCA* positive or negative; no restriction on number of lines of prior therapy.

- [4] Have a performance status (PS) of 0 or 1 on the Eastern Cooperative Oncology Group (ECOG) scale (Oken et al. 1982).
- [5] Have discontinued all previous treatments for cancer and recovered from acute effects of therapy. Patients must be discontinued from previous treatments, as per below:

Previous Treatment	Length of Time Prior to First Dose of Prexasertib
Cytotoxic therapies or targeted agents that are small molecule inhibitors	≥21 days or ≥ 5 half-lives, whichever is shorter
Biologic agents that are large molecules including immunotherapy	≥28 days
Investigational agents	≥28 days. If the agent has a long half-life (e.g. >2 weeks), then 3 months or 5 half-lives (whichever is longer) should have passed
Radiotherapy	
Limited-field radiotherapy with palliative intent	≥14 days
Other radiotherapy	≥28 days
Major surgery, excluding biopsy	≥28 days

- [6] Have at least 1 measurable lesion using standard techniques by Response Evaluation Criteria in Solid Tumors (RECIST) version 1.1 (Eisenhauer et al. 2009).
- [7] Have given written informed consent prior to any study-specific procedures and agree and are able to follow the requirements of the protocol.
- [8] Are of an acceptable age to provide informed consent according to the local regulations and are at least 18 years of age.
- [9] Have adequate organ function, as defined below. These values must be met during the baseline visit (prior to biopsy) as well as predose Cycle 1 Day 1:

System	Laboratory Value
Hematologic	
ANC	≥1.5×10 ⁹ /L
Platelets	≥100×10 ⁹ /L
Hemoglobin	≥9 g/dL
Note: transfusions to increase a patient's hemoglobin level or initiation of erythropoietin or G-CSF therapy to meet enrollment criteria are not allowed in the 14 days preceding the first dose of study drug. If a patient receives transfusions, erythropoietin, or G-CSF therapy ≥14 days prior to the first dose, the hematologic criteria listed above must be met following the 14 day window and prior to the first dose of study therapy.	
Hepatic	
Direct bilirubin	≤1.5×ULN
ALT and AST	≤3×ULN OR ≤5×ULN if the liver has tumor involvement
Renal	
Serum creatinine OR	<1.5×ULN OR
Measured creatinine clearance OR	≥40 mL/min/1.73 m ²
Calculated creatinine clearance	
Albumin	
Albumin	>30 g/L OR 25-30 g/L and the value does not decrease across 2 readings separated by ≥14 days (without an intravenous albumin infusion)

Abbreviations: ALT = alanine aminotransferase; ANC = absolute neutrophil count; AST = aspartate aminotransferase; G-CSF = granulocyte colony stimulating factor; ULN = upper limit of normal.

- [10] Women of child-bearing potential participating must agree to use one highly effective (less than 1% failure rate) method of contraception or use a combination of two effective methods of contraception during treatment with study drug and for at least 12 weeks following the last dose of study drug.

Note: Unless not allowed by local regulations, women of child-bearing potential who are abstinent (if this is complete abstinence, as their preferred and usual lifestyle) or in a same sex relationship (as part of their preferred and usual lifestyle) must agree to either remain abstinent or stay in a same sex relationship without sexual relationships with males. Periodic abstinence (e.g., calendar, ovulation, symptothermal, postovulation methods), declaration of abstinence just for the duration of a trial, and withdrawal are not acceptable methods of contraception.

- [11] Women of child-bearing potential participating must test negative for pregnancy prior to initiation of treatment as indicated by a negative pregnancy test at the screening visit (prior to biopsy) and within 24 hours prior of drug exposure.
- [12] Cohorts 1-3: Have documented test results assessing alterations in the *BRCA1* and *BRCA2* genes by a local laboratory prior to receiving study treatment. Results from either a blood or tissue based test are acceptable.
- [13] Must be able and willing to undergo mandatory tumor biopsy which will be collected following determination of eligibility and before treatment (≤ 28 days before C1D1). Note that the biopsy may be collected prior to the predose Cycle 1 Day 1 pregnancy test and labs. Tumor tissue obtained from a prior biopsy may be permitted for the pretreatment sample after discussion and agreement between Lilly clinical research physician (CRP) / clinical research scientist (CRS) and investigator if a patient has not received any therapies for the disease between the time biopsy was obtained to start of prexasertib treatment. The decision to use a tumor tissue sample from a prior biopsy will be documented in writing.

6.2. Exclusion Criteria

Patients will be excluded from the study if they meet **any** of the following criteria:

- [14] Cohorts 1-3: Have previously received all of the following agents at any time in the platinum-resistant setting: gemcitabine, PEGylated liposomal doxorubicin, and paclitaxel. It is acceptable to have received 1 or 2 of these agents for platinum-resistant disease.
- [15] Have non-epithelial or mixed epithelial/non-epithelial tumors (including malignant mixed Müllerian tumors), ovarian tumors with low malignant potential (borderline tumors), endometrioid, clear cell, mucinous or low-grade serous carcinomas or not otherwise specified (NOS) ovarian tumors.

- [16] Have known central nervous system (CNS) malignancy or metastasis. Patients with treated brain metastases that have been CNS recurrence-free for 1 year prior to study treatment may be considered if approved by the Lilly CRP/CRS.
- [17] Have prior malignancies unless approved by the Lilly CRP/CRS. For instance, patients with carcinoma in situ of any origin and patients with prior malignancies who are in remission and whose likelihood of recurrence is very low, as judged by the Lilly CRP/CRS, may be eligible for this study.
- [18] Are currently enrolled in a clinical study involving an investigational product or any other type of medical research judged not to be scientifically or medically compatible with this study.
- [19] Have previously completed or withdrawn from this study or any other study investigating prexasertib or a CHK1 inhibitor or have shown hypersensitivity to the study drug or excipients.
- [20] Have a known serious medical condition (e.g., active infection, increased risk of bleeding events) that, in the opinion of the investigator, would compromise the patient's ability to adhere to the protocol or tolerate the study treatment.
- [21] Have at least one of the following:
- history of abdominal fistula or gastrointestinal (GI) perforation
 - intra-abdominal abscess within last 3 months prior to the first dose of study drug
 - a radiographically confirmed bowel obstruction (including sub-occlusive disease) within 3 months prior to the first dose of study drug.
- [22] Have a symptomatic human immunodeficiency virus (HIV) infection or symptomatic activated/reactivated hepatitis A, B, or C (screening is not required).
- [23] Have a serious cardiac condition, such as:
- symptomatic congestive heart failure or any uncontrolled cardiac disease
 - New York Heart Association Class III/IV heart disease
 - unstable angina pectoris
 - symptomatic or poorly controlled cardiac arrhythmia
 - myocardial infarction within the last 3 months
 - have a QT interval using Fridericia's correction (QTcF) of >480 msec on more than one electrocardiogram (ECG) obtained during the baseline (screening) period
 - family history of long-QT syndrome.
- [24] Have a history of prior radiotherapy to the whole pelvis.
- [25] Have chronic daily treatment with corticosteroids (dose >10 mg/day methyl-prednisolone equivalent), excluding inhaled and topical steroids.
- [26] Have known factors that may increase the risk of infection while on study drug treatment. These may include, but are not limited to, an indwelling peritoneal catheter or open wounds. Catheters for vascular access are permitted.

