Adverse Events Collection/ CTCAE Grading			X		CTCAE version 4.0.
Concomitant Medication Notation			X		Includes information on over-the-counter and prescription analgesics
Laboratory/ Diagnostic Tests	Hematology			X	See Appendix 2
	Chemistry			X	See Appendix 2
	Urinalysis			X	See Appendix 2
	CA-125			X	Centrally assessed.
	Pregnancy test		X		Women of childbearing potential must have negative pregnancy test prior to biopsy (to confirm eligibility) and a negative pregnancy test within 24 hours prior to drug exposure. Either a urine or serum test is acceptable.
	ECG			X	Single local ECG.
	Pretreatment biopsy		X		May be performed at any time, but sample should be taken only after study eligibility is confirmed.

Schedule of Inclusion and Baseline Assessments

Study Period		Baseline			
Cycle		Baseline (Screening)			
Visit		0			
Duration		Up to 42 days			
Relative Day C1D1		≤42	≤28	≤14	
Procedure Category	Procedure				Comments
Health Outcome Assessments	Worst Pain NRS		X		One question assessing worst pain will be administered by site personnel and completed by the patient prior to extensive interaction with site staff.
	NFOSI-18		X		NFOSI-18 will be administered by site personnel and completed by the patient prior to extensive interaction with site staff.

Abbreviations: C1D1 = Cycle 1 Day 1; CTCAE = Common Terminology Criteria for Adverse Events; ECG = electrocardiogram; ECOG = Eastern Cooperative Oncology Group; EOI = end of infusion; IV = intravenous; NRS = numeric rating scale; NFOSI-18 = National Comprehensive Cancer Network – Functional Assessment of Cancer Therapy – Ovarian Symptom Index-18; RECIST = Response Evaluation Criteria in Solid Tumors version 1.1 (Eisenhauer et al. 2009).

Table JTJN.2. On-Study Treatment Schedule of Activities

Study Period		Cycle				
Cycle/Visit		1		2-n		
Duration		28 days		28 days		
Relative Day within Dosing Cycle		1	15	1	15	
Procedure Category	Procedure					Notes
Physical Examination	Physical examination	X		X		Includes weight and calculated BSA. May be completed up to 7 days prior to treatment infusion.
	Vital signs	X	X	X	X	Includes blood pressure, pulse, and temperature. Complete before each treatment infusion.
	ECOG performance status	X		X		Complete before treatment infusion on Day 1.
Laboratory/ Diagnostic Tests	Hematology	X	X	X	X	May be drawn up to 3 days before the day of dosing. Additional assessments may be obtained at the discretion of the investigator.

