	Chemistry	X		X		May be drawn up to 3 days before the day of dosing. Additional assessments may be obtained at the discretion of the investigator.
	Pregnancy test	X		X		Applies only to women of childbearing potential. Where required by local law/ regulation or institutional guidelines, perform once every 28 days (± 7 days). Either a urine or serum test is acceptable.
	CA-125	X		X		May be drawn up to 3 days before the day of dosing
	PK sampling	X		X		Sparse PK sampling will be conducted over multiple cycles of therapy (see Appendix 4 for additional details).
	Stored blood sample for pharmacogenetics	X				Collect once. Sample can be collected at any time if not collected on Day 1 of Cycle 1.
	Plasma biomarker sample	X		X		Collect only in Cycles 1 and 4. May be drawn up to 3 days before the day of dosing.
	ECG	X	X	X	X	Single local ECG collected at each time point only. Cycle 1 Day 1 and Cycle 2 Day 1: predose, within 15 min after EOI. Cycle 1 Day 15, Cycle 2 Day 15, and Cycle 3-n: Day 1 and 15 prior to each dose. Additional ECGs may be obtained at the discretion of the investigator. When ECGs and PK are required at the same time point, the ECG should be obtained prior to the PK draw.
	Optional tumor biopsy			X		Can occur at any time during patient's treatment. Patients should have adequate neutrophils and platelets prior to biopsy. See Section 9.8.1.

On-Study-Treatment Schedule of Activities

Study Period		Cycle					
		1		2-n			
Cycle/Visit		1		2-n			
Duration		28 days		28 days			
Relative Day within Dosing Cycle		1	15	1	15		
Procedure Category	Procedure					Notes	
Tumor Assessment	Radiologic imaging according to RECIST version 1.1 and tumor measurement (palpable or visible)		X				Perform approximately every 8 weeks (±1 week) up to 1 year, thereafter every 12 weeks (±1 week). The first scan should be approximately 8 weeks (±1 week) from Cycle 1 Day 1. The 8-week/12-week scanning interval should be maintained even if cycles are delayed. As a result, the scans may not always occur at the end of a cycle. The same method of imaging used at baseline should be used for each subsequent assessment. Scans should also be obtained as clinically indicated. Scans to confirm responses may be performed sooner than 8 weeks, but should be at least 4 weeks following the initial observation of an objective response. The next scan should be 8 weeks (±1 week) following the confirmatory scan.

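### The QTcF exclusion needs more than one prolonged screening ECG, but the schedule provides one and nothing requires a repeat

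*Protocol*

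**What the plan says.** Exclusion [23] in Protocol Section 6.2 opens with "Have a serious cardiac condition, such as" and then lists examples. One is a QTcF "of >480 msec on more than one electrocardiogram (ECG) obtained during the baseline (screening) period".

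The baseline schedule, Table JTJN.1, has one ECG entry, in the column for the 14 days before Cycle 1 Day 1. Its comment reads "Single local ECG". The same table says of the pretreatment biopsy that the "sample should be taken only after study eligibility is confirmed". Protocol Section 7.2 assigns a patient to a cohort once all enrollment criteria are met.

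The next scheduled ECG is in the on-treatment schedule, Table JTJN.2: predose on Cycle 1 Day 1. That table's ECG row also carries the sentence "Additional ECGs may be obtained at the discretion of the investigator". The screening row has no such sentence.

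**The concern.** A rule that needs two long readings is paired with a schedule that produces one. Unless a site adds an ECG that the protocol does not call for, the QTcF item cannot be met, however long the single reading is. Two patients with the same first reading could then be handled differently at different centers, one excluded after a voluntary repeat and the other enrolled without one.

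What is at stake is patient safety at entry. The protocol plainly regards QT prolongation as a hazard: [23] also excludes a family history of long-QT syndrome, and Section 7.7 advises against more than one QT-prolonging medication on dosing days and asks for normal electrolytes. The estimate of ORR, the futility rules and the analysis sets are unaffected.

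**Working it through.** The plan states no figure to reproduce here. The check is a count, followed by a reading of every place that could supply the missing ECG.

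**Count**

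- ECGs above 480 msec needed by the QTcF item in [23]: more than one, so at least 2.
- ECGs scheduled in the baseline (screening) period, Table JTJN.1: 1.
- Shortfall: 2 − 1 = 1.

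**Is a repeat required elsewhere?**

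- Protocol Section 6.4 says that certain repeated screening tests do not count as rescreening. It requires no repeat.
- Protocol Section 9.4.1 refers back to the Schedule of Activities for ECGs and adds nothing.
- Protocol Section 7.4 and Table JTJN.7 contain no QTcF limit for withholding or delaying a dose.
- SAP Section 5.13.6 covers only how ECGs are summarized.

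**Does the predose Cycle 1 Day 1 ECG serve as the second reading?**

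- It is listed under Cycle 1 in Table JTJN.2. The period named in [23] carries the label of Visit 0 in Table JTJN.1.
- Cohort assignment and a new biopsy both presuppose that eligibility has been confirmed. If the Day 1 ECG could complete the exclusion, a patient could have a mandatory biopsy and only then prove ineligible.
- Where Day 1 values are meant to count, the protocol says so. For organ function, inclusion [9] states "These values must be met during the baseline visit (prior to biopsy) as well as predose Cycle 1 Day 1". Inclusion [11] asks for a negative pregnancy test at screening and again within 24 hours before dosing.
- Where a second reading is wanted, the protocol says that too. An albumin of 25-30 g/L qualifies only if "the value does not decrease across 2 readings", with an interval of at least 14 days.
- For QTcF it does neither.

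**Size**

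The documents give no frequency of first readings above 480 msec. Taking 1% to 5% as an assumption:

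| Patients enrolled | at 1% | at 5% |
|---|---|---|
| 180 (protocol maximum) | 180 × 0.01 = 1.8 | 180 × 0.05 = 9.0 |
| 80 (four cohorts at the approximate minimum: 4 × 20) | 80 × 0.01 = 0.8 | 80 × 0.05 = 4.0 |

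At the maximum, about 2 to 9 patients would have a long first reading. The mandatory repeat would add about the same number of local ECGs across the study.

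**The case against.** The strongest reply is that every patient does have a second ECG before the first dose, on Cycle 1 Day 1, and that the line between baseline and Day 1 is not sharp. A footnote to Table JTJN.7 places baseline before dosing on that day. SAP Section 5.1 takes the last assessable value before dosing as the safety baseline. The screening ECG column has no lower bound that excludes Day 1. A note to Table JTJN.2 lets one laboratory draw serve both visits. Inclusion [9] and [11] keep some conditions open until dosing, and [13] lets the biopsy precede those checks.

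These texts show that some eligibility checks run late, but they do not settle the ECG question. The footnote defines baseline for recovery from toxicity, and the SAP definition is for safety summaries. The note to Table JTJN.2 concerns laboratory tests, and the late checks named in [13] are the pregnancy test and laboratory tests. No text applies the 480 msec limit to the Day 1 ECG.

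A second reply is that the wording of [23] implies a confirmatory repeat, that the single-ECG comment may mean only that replicates are not needed, and that nothing forbids a repeat. This is fair: a sensible site may well repeat the test. But the repeat remains a choice.

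A third reply is that other safeguards exist. The list in [23] is illustrative. Exclusion [20] lets the investigator exclude a patient with a known serious condition thought to compromise the ability to "adhere to the protocol or tolerate the study treatment". ECGs precede every dose, and Section 7.4 allows dose delays on clinical grounds. All of this stands, so protection is partial rather than absent, though each safeguard depends on judgement when it comes to acting on a long QTcF.

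The objection to the size also has force. The 1% to 5% rate is assumed, and the count of long first readings is not a count of patients wrongly enrolled. Some sites will repeat anyway, and patients whose repeat is 480 msec or less are eligible either way. The number whose eligibility would change is unknown and could be zero.

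**Conclusion.** The concern holds. As written, the QTcF item in [23] cannot be triggered by the ECG scheduled in screening, and no text requires the second one. A patient whose only screening QTcF is above 480 msec can be enrolled without breaching that item.

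The shortfall of one ECG is a matter of counting. The conclusion rests on reading the baseline (screening) period as Visit 0 of Table JTJN.1, which is the natural reading given the table's own label. The figure of 2 to 9 patients depends on the assumed rate and full enrollment of 180, and is an upper-end illustration. Because the affected group is likely small and discretionary safeguards exist, this is a defect that should be corrected, not one that undermines the trial.

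**What to change.** Add to the comment in the ECG row of Table JTJN.1, with a cross-reference in exclusion [23]:

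*If QTcF on the screening ECG is >480 msec, a repeat ECG must be obtained within the screening period, before enrollment and biopsy; the patient is excluded if the repeat is also >480 msec.*

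This leaves both the limit and the principle of confirmation unchanged. The cost is one sentence, one cross-reference and one extra local ECG for each patient with a long first reading. No analysis or sample-size text needs to change.
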